### 9.5 BLINDING AND PREVENTION OF BIAS

There is no blinding for the Part 1 of the study. However, all subjects, Investigators and their staff, and all Sponsor/CRO personnel involved in the management of the study will be blinded to treatment assignments for the Part 2 of the study. Treatment unblinding for the study will occur after all clinical data have been received, data inconsistencies have been resolved, and the database is locked, except for the interim analysis or for safety reasons on a case-by-case basis (i.e., emergency unblinding).

## 9.6 INTERIM ANALYSIS (IA)

[REDACTED]

[REDACTED]

[REDACTED]

- [REDACTED]
- [REDACTED]
- [REDACTED]
- [REDACTED]
- [REDACTED]

## 9.7 GENERAL STATISTICAL CONSIDERATIONS

All collected study data will be presented in subject data listings. Statistical analyses will be performed using SAS® for Windows, version 9.4 or later. Descriptive statistics (n, mean, standard deviation, median, minimum and maximum) will be calculated for continuous variables. Frequencies and percentages will be presented for categorical variables.

## 9.8 ANALYSIS POPULATIONS

The details of the analysis populations to be used for the study are described in the below sections.

[REDACTED]

[REDACTED]

[REDACTED]

[REDACTED]

[REDACTED]

[REDACTED]

### 9.9 HANDLING OF MISSING DATA

All efforts will be made to avoid missing data; however, there will be no imputation of missing data for this early phase study and all summaries will be based on observed data only.

[REDACTED]

[REDACTED]

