### 3.3 PHASE II (PART 2) STUDY DESIGN

Phase II (Part 2) of this study is a multi-center, double-blind, randomized, vehicle-controlled study of the safety and efficacy of topically applied AMTX-100 *CF3* in adult patients with Mild to Moderate AD. Sixty (60) subjects will be enrolled in 2 groups of AMTX-100 *CF3* and placebo (vehicle). The subjects will be randomized in a 1:1 ratio, thus thirty (30) subjects will be randomized in each group (Group A: Treatment 1.1% w/w of AMTX-100 *CF3*) and Group B: placebo (vehicle 0% w/w)). Each enrolled subject, after screening and randomization, will receive AMTX-100 *CF3* 1.1% w/w or placebo (vehicle) to be applied twice daily to all treatable AD lesions (excluding the scalp, face, eyes, eyelids, hands, palms, feet, groin, genitals or in the axillae) for 28 consecutive days.

The study groups are as follows:

- **Group A:** AMTX-100 *CF3* dose concentration (1.1% w/w), topically applied twice a day for 28 consecutive days to all treatable AD affected areas
- **Group B:** Placebo (Vehicle) (0% w/w), topically applied twice a day for 28 consecutive days to all treatable AD affected areas

[REDACTED]

[REDACTED]

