### 5.2 SUBJECT PREMATURE WITHDRAWAL FROM THE STUDY

[REDACTED]

Reasons for subject withdrawal/discontinuation may constitute one of the following:

- Subject chooses to withdraw
- Subject is withdrawn due to an AE
- Pregnancy or positive pregnancy test
- Lost to follow-up
- The Investigator determines that it is in the subject's best interest
- Excessive protocol deviations, as determined by the Investigator or the Sponsor

- Discontinuation of the study by the Sponsor

[REDACTED]

- [REDACTED]
- [REDACTED]
- [REDACTED]

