**9.2.2 PHASE II (PART 2) STUDY OUTCOME MEASURES**

**9.2.2.1 Primary Efficacy Outcome Measure:**

- Proportion of responder subjects at Day 28, defined as subjects with both Validated Investigator Global Assessment for Atopic Dermatitis (vIGA-AD™) score of 0 (clear) or 1 (almost clear) (on a 5-point scale) and a reduction of  $\geq 2$  points from baseline

Note: Subjects who receive rescue treatments will be considered non-responders

[REDACTED]

■ [REDACTED]

■ [REDACTED]

■ [REDACTED]

■ [REDACTED]

■ [REDACTED]

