### 9.12 STATISTICAL METHODS

A Statistical Analysis Plan (SAP) will be developed and approved before the database is locked. The SAP will present the detailed statistical methodology to be used in analyzing the efficacy and safety data from this trial. [REDACTED]

[REDACTED]

[REDACTED]

[REDACTED]

[REDACTED]

[REDACTED]

[REDACTED]

[REDACTED]

[REDACTED]

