## 9.14 ANALYSES FOR THE OUTCOMES OF THE PART 2 STUDY

### Efficacy Summaries

The efficacy evaluable population will be the primary analysis population for the analysis of the efficacy outcome measures of the Part 2 study. All the primary and secondary outcome measures will be analyzed according to the variable type:

- [REDACTED]

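### As readable, the Part 2 plan most naturally drops a non-rescued subject with no Day 28 vIGA-AD score from the primary responder proportion but counts a rescued subject as a failure; outcome-related missingness would then bias the comparison

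*Protocol*

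**What the plan says.** Protocol 9.2.2.1 defines the Part 2 primary endpoint as "Proportion of responder subjects at Day 28, defined as subjects with both Validated Investigator Global Assessment for Atopic Dermatitis" score 0 or 1 and a fall of at least 2 points from baseline. Its one readable note on classification is "Subjects who receive rescue treatments will be considered non-responders".

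Protocol 9.9 says that "there will be no imputation of missing data for this early phase study and all summaries will be based on observed data only". No exception for the primary endpoint is readable. Section 9.7 adds only that "Frequencies and percentages will be presented for categorical variables", so the denominator is not stated.

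Section 5.2 foresees subjects leaving early, by choice, by loss to follow-up or because "Subject is withdrawn due to an AE". Section 9.14 states: "The efficacy evaluable population will be the primary analysis population for the analysis of the efficacy outcome measures of the Part 2 study". The definition of that population in 9.8 is redacted, as are the text after the note in 9.2.2.1 and the Part 2 methods in 9.12 and 9.14. Section 9.12 defers detail: "The SAP will present the detailed statistical methodology to be used in analyzing the efficacy and safety data from this trial". The supplied SAP covers Part 1 only; its section 7.4 repeats the rule of 9.9.

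**The concern.** A subject who is doing badly and receives rescue counts as a failure. A subject who is doing equally badly and leaves without rescue, and so has no Day 28 score, most naturally disappears from numerator and denominator alike. Similar outcomes would then be treated differently in the primary comparison of a randomised, double-blind trial.

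The text also admits a second reading: a subject without a score has not met the responder definition and so is a non-responder. That fits the observed-data rule poorly, but it is possible. Two analysts could therefore obtain different primary results from the same data, and a choice made after unblinding would be open to challenge. With 30 per arm, one missing subject is 1/30 = 3.3% of a randomised arm.

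**Working it through.** **Inputs.** From the documents: 60 subjects allocated 1:1, "thus thirty (30) subjects will be randomized in each group" (3.3), and 60/2 = 30 agrees. The number was set by clinical judgment (9.3), so there is no power calculation to reproduce, and no response or dropout rate is readable. Assumed for illustration: 8 active and 3 vehicle responders are seen, none of them rescued, and m_A and m_V subjects have no Day 28 score and no rescue. All randomised subjects are used as the base, because the efficacy evaluable definition is redacted. P-values are two-sided Fisher exact.

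**Step 1: the two readings.**
- Missing as failure: 8/30 − 3/30 = 26.7% − 10.0% = 16.7 points (p = 0.18), whatever the number missing.
- Observed only: 8/(30 − m_A) − 3/(30 − m_V).

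| Missing active/vehicle | Observed-only calculation | Difference (points) | Gap G from 16.7 | p |
|---|---|---|---|---|
| 1/1 | 8/29 − 3/29 | 17.2 | +0.6 | 0.18 |
| 3/3 | 8/27 − 3/27 | 18.5 | +1.9 | 0.175 |
| 6/3 | 8/24 − 3/27 | 22.2 | +5.6 | 0.09 |
| 3/9 | 8/27 − 3/21 | 15.3 | −1.3 | 0.30 |

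These are gaps between two readings, not errors against the truth.

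**Step 2: error of each rule.** Let o be the observed response rate in an arm, and let missing subjects in that arm respond at r × o, with the same r in both arms. The all-randomised difference is 16.7 + r × G, where G = (o_A × m_A − o_V × m_V)/30. Observed-only then errs by (1 − r) × G and missing-as-failure by −r × G. The absolute errors are equal at r = 0.5; observed-only is worse below that and missing-as-failure is worse above it.

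| Missing | r | Observed-only error | Missing-as-failure error |
|---|---|---|---|
| 3/3 | 0 | +1.9 | 0 |
| 3/3 | 0.5 | +0.9 | −0.9 |
| 3/3 | 1 | 0 | −1.9 |
| 6/3 | 0 | +5.6 | 0 |
| 6/3 | 0.5 | +2.8 | −2.8 |
| 6/3 | 1 | 0 | −5.6 |

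The last row matters: at r = 1, where missingness is unrelated to outcome within arm, the unbalanced 6/3 pattern leaves observed-only with no error.

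**Step 3: r differing by arm, at 3/3.**
- Missing active subjects all fail and missing vehicle subjects respond at the observed rate of 3/27. Truth = 8/30 − (3 + 3 × 3/27)/30 = 15.6. Observed-only errs by +3.0 and missing-as-failure by +1.1.
- The reverse. Truth = (8 + 3 × 8/27)/30 − 3/30 = 19.6. The errors are −1.1 and −3.0.

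So the observed-only bias can go either way.

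**Step 4: limits at 3/3.** Over every possible outcome of the six missing subjects, the difference runs from 8/30 − 6/30 = 6.7 points (p = 0.76) to 11/30 − 3/30 = 26.7 points (p = 0.03).

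**Step 5: cost of missing-as-failure.** Suppose the true rates are 26.7% and 10.0% and missingness is unrelated to outcome. The expected difference is 26.7 × 27/30 − 10.0 × 27/30 = 15.0 at 3/3, and 26.7 × 24/30 − 10.0 × 27/30 = 12.3 at 6/3. With more missing on vehicle it can grow instead: at 3/9 it is 26.7 × 27/30 − 10.0 × 21/30 = 17.0.

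**The case against.** The strongest reply is that much of the relevant text is redacted. The efficacy evaluable definition, the text after the primary endpoint note and the Part 2 methods are not readable, and no Part 2 SAP is supplied. A reader might infer that the plan has no rule for these subjects. The documents do not support that: a rule may exist there. What stands is narrower. Section 9.9 does not leave a gap; it states a rule, and it does so without qualification. The redacted blocks after it sit where the contents list places 9.10, so the readable sentence may be all of 9.9. Any non-responder rule elsewhere would need reconciling with it.

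The population also limits the remedy. If the efficacy evaluable definition already requires a Day 28 score, these subjects are removed by the population and not by 9.9. Reclassifying them would then change nothing in the primary analysis.

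Two further inferences are tempting and do not hold. One is that unequal dropout by itself biases the observed-only difference; Step 2 shows no error at r = 1 with 6/3 missing. The other is that counting missing as failure is always the less biased rule; it is worse above r = 0.5, and no figure in the documents places r.

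It is also fair that rescue is a recorded event while a missing score is absent data, so treating them differently is not a contradiction. Treatment lasts 28 days with weekly visits, and missed visits are to be made up (4.4), so missingness may be low. In the illustration, neither rule crosses p = 0.05 in any pattern. The Part 1 SAP shows only that the wording can pass into a SAP unchanged; it has no randomised responder endpoint.

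**Conclusion.** The point holds on the readable text. Sections 9.9 and 9.2.2.1 together most naturally omit a non-rescued subject without a Day 28 score while a rescued subject counts as a failure. The active-versus-vehicle difference can then be biased in either direction if missingness is related to outcome within arm, and differing amounts or causes of missingness between arms change the size and sign.

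The actual size cannot be known from the documents. Under the assumed 8 versus 3 responders, the two readings differ by about half a point to two points when missingness is low and balanced (1/1 to 3/3), and by 5.6 points at 6/3. This rests on the assumed counts, on 30 per arm as the base, and on no contrary rule in the redacted text. Severity is low to moderate: a cheap improvement, not a flaw that undermines the trial.

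**What to change.** Before any unblinding, amend 9.2.2.1, 9.9 and the Part 2 SAP as follows:

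1. State, as an exception to the observed-data rule, that a missing Day 28 vIGA-AD score counts as non-response in the primary responder analysis, or reconcile 9.9 with any rule already in the redacted text. If the efficacy evaluable definition already requires a Day 28 score, apply this in the all-randomised analysis instead.
2. Keep the observed-data analysis as supportive.
3. Report missing Day 28 scores by arm and reason.
4. If not already planned, add an all-randomised analysis by assigned arm and a tipping-point table over the possible outcomes of the missing subjects. These two help whatever the redacted text says.

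The cost is wording, one missingness table and two sensitivity outputs from data already collected; visits, sample size and the primary population do not change. The downside is slightly lower response rates and, if missingness is unrelated to outcome, a distorted difference, usually a smaller one (Step 5). Items 2 and 4 would show this.

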### 9.11 TYPE I ERROR RATE ADJUSTMENT

This is an early phase study and there is no need for adjustment of Type I error rate.

### 9.12 STATISTICAL METHODS

A Statistical Analysis Plan (SAP) will be developed and approved before the database is locked. The SAP will present the detailed statistical methodology to be used in analyzing the efficacy and safety data from this trial. [REDACTED]

[REDACTED]

[REDACTED]

[REDACTED]

[REDACTED]

[REDACTED]

[REDACTED]

[REDACTED]

[REDACTED]

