## 12 DATA SAFETY MONITORING COMMITTEE (DSMC)

In Phase I (Part 1) of the study, the study will be monitored by an independent Data Safety Monitoring Committee (DSMC) to ensure patient safety. The CRO is responsible for the overall management of the DSMC, including development of its charter and membership selection. The DSMC will be managed in conformance with the FDA guidelines for DSMC independence, management, and oversight.

[REDACTED]

[REDACTED]

[REDACTED]

[REDACTED]

- [REDACTED]
- [REDACTED]
- [REDACTED]
- [REDACTED]

[REDACTED]

In Phase II (Part 2) of the study, the DSMC will consider safety data generated during Part 2 of the study and to make recommendations about the IA.

[REDACTED]

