1. INTRODUCTION

This Statistical Analysis Plan describes the planned analyses and reporting for the Phase I (Part 1) clinical trial protocol AMTX100-AD-01, conducted by Amytrx Therapeutics, Inc. The reader of this Statistical Analysis Plan (SAP) is encouraged to review the complete protocol and amendments as this plan contains only a limited overview of protocol information. The main objectives of this plan are to provide details pertaining to statistical methodology, data conventions, and processes used for the analysis of data from this trial.

The format and content of this SAP are structured to provide sufficient detail to meet the requirements specified by the International Council on Harmonization (ICH) E9: Guidance on Statistical Principles in Clinical Trials. All work planned and presented in this Statistical Analysis Plan will follow the ethical guidelines published by the American Statistical Association (ASA).

The following documents were reviewed in preparation of this Statistical Analysis Plan:

- Final protocol 2.0/ 20 Jan 2020
- ASA Ethical Guidelines for Statistical Practice (2016)
- The Royal Statistical Society: Code of Conduct (2014)
- ICH Guidance on the Structure and Content of Clinical Study Reports (ICH E3, 1996)
- ICH Guidance on the Structure and Content of Clinical Study Reports (ICH E3(R1), 2013)
- ICH Guidance on the Statistical Principles for Clinical Trials (ICH E9, 1998)
- ICH Guidance on the Statistical Principles for Clinical Trials (ICH E9(R1), 2017)

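### Does a database-lock deadline for the SAP let the Part 2 methods be written after unblinded interim results exist?

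*Protocol*

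**What the plan says.** Protocol section 9.12 gives the timing, "A Statistical Analysis Plan (SAP) will be developed and approved before the database is locked", and the scope: "The SAP will present the detailed statistical methodology to be used in analyzing the efficacy and safety data from this trial". The opening of section 9 also defers detail to the SAP, without a date.

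Section 9.5 holds Part 2 unblinding until the data are in, inconsistencies are resolved, "and the database is locked, except for the interim analysis or for safety reasons on a case-by-case basis". The same section states that "all Sponsor/CRO personnel involved in the management of the study will be blinded to treatment assignments for the Part 2 of the study". Section 12 says that in Part 2 "the DSMC will consider safety data generated during Part 2 of the study and to make recommendations about the IA".

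The supplied SAP defines its own scope in its Introduction: "This Statistical Analysis Plan describes the planned analyses and reporting for the Phase I (Part 1) clinical trial protocol AMTX100-AD-01". For Part 2, protocol section 9.14 names the population: "The efficacy evaluable population will be the primary analysis population for the analysis of the efficacy outcome measures of the Part 2 study".

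In the public copy the body of 9.6 (interim analysis), the population definitions in 9.8, the rest of 9.12, the analysis bullets in 9.14 and much of section 12 are blacked out.

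**The concern.** The usual safeguard is that the methods of a blinded comparison are settled before anyone can know results by arm. Database lock normally provides this, because unblinding follows lock. Here the interim analysis is an express exception, so lock no longer marks the first moment at which results by arm can exist. The one SAP in hand covers only the open-label Part 1, and so settles nothing for Part 2.

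Set together, these points seem to leave a window between interim unblinding and lock in which the Part 2 SAP could still be approved. If its authors knew the interim results, they could pick whichever open detail suited them. The definition of the efficacy evaluable population is the obvious candidate. The stake would be the false-positive rate of the Part 2 vehicle comparison, in a trial of 60 subjects for which section 9.11 plans no type I error adjustment.

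**Working it through.** The plan gives no figure to reproduce: section 9.3 rests the 60 subjects on clinical judgment, and no alpha, response rate or interim size is readable. The check is first one of sequence, then one of size.

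**Sequence allowed by the readable text**

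1. Part 2 starts, double-blind (9.5).
2. Interim unblinding occurs (9.5, exception).
3. The SAP is approved at any time up to lock (9.12).
4. The database is locked and final unblinding follows (9.5).

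Step 3 after step 2 breaches nothing readable. For that order to bias the result, two further conditions must both hold.

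**Condition A: someone who writes or approves the SAP sees interim results by arm.** Section 9.5 keeps the sponsor and CRO staff managing the study blinded throughout Part 2. Its exception concerns when unblinding happens and does not say that those staff are unblinded. Section 12 gives the role of recommending on the interim to the DSMC. No readable sentence gives SAP authors access.

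**Condition B: a consequential method is still open.** The readable protocol already fixes:

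- the primary responder rule (vIGA-AD 0 or 1 at Day 28 with a drop of at least 2 points), with rescued subjects counted as non-responders (9.2.2.1);
- no imputation, observed data only (9.9);
- no type I error adjustment (9.11);
- the primary analysis population for efficacy (9.14).

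The one detail proposed as open is the definition of that population. Section 9.8 says the population details are set out in its own subsections. The definition therefore sits in the protocol and is only hidden from view. It is not deferred to the SAP.

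**Size if both conditions are nevertheless assumed**

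Assumed inputs: two-sided 0.05; 30 per arm (from 3.3); equal response of 10, 20 or 30% in both arms; a rival population definition that drops 10 or 20% of subjects at random; the definition with the smaller uncorrected chi-square p at the interim is carried to the final test. Each setting uses 200,000 simulated null trials, so the Monte Carlo standard error is √(0.05 × 0.95 / 200,000) = 0.0005, or 0.05 points.

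| How the definition is chosen | Final test | Type I error |
|---|---|---|
| Fixed in advance, either definition | chi-square | 4.4–5.4% |
| Picked at interim, 10 per arm | chi-square | 5.6–6.1% |
| Picked at interim, 15 per arm | chi-square | 5.9–6.5% |
| Picked at interim, 20 per arm | chi-square | 6.1–6.8% |
| Picked without sight of results by arm | chi-square | 4.9–5.1% |
| Smaller of the two final p values (upper bound) | Fisher | at most 4.3% |

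At 15 per arm the excess over the higher of the two fixed values is 0.5–1.3 points. A fresh run of these scenarios reproduced the figures to within about 0.1 point. The excess appears only when the chooser sees results by arm and the final test is the uncorrected chi-square.

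**The case for a change.** The strongest opposing case is that a plan should not depend on who happened to see what. A deadline before interim unblinding would make the question moot, at the cost of one sentence and an earlier sign-off. Section 9.5 blinds those involved in managing the study, and the readable text does not say whether SAP authors and approvers belong to that group. The supplied SAP cannot stand in for a Part 2 plan. It was written against protocol 2.0, and its section 2.1 still describes Part 2 with three concentrations and up to 70% BSA, where the current protocol has one concentration against vehicle and up to 30%.

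Part of this stands. The literal reading of 9.12 beside 9.5 is correct, and an earlier deadline would be tidier. It does not amount to a defect. The argument needs the absence of an earlier date or access rule, yet the text directly after the quoted sentences in 9.12 and the whole body of 9.6 are blacked out. What is hidden for that reason cannot be counted as missing. The same applies to a Part 2 SAP that is not among the supplied files: the Part 1 document says nothing either way about when the Part 2 plan was or will be approved.

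**Conclusion.** The concern does not hold. Approval of the SAP before lock conflicts with no readable statement. Followed as written, the plan keeps the study's managers blinded, gives the DSMC the interim role, and fixes the main Part 2 efficacy choices in the protocol. Harm would require a SAP author or approver to see results by arm, which nothing readable says happens. It would also require the population definition to be open, which section 9.8 contradicts by placing it in the protocol.

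If both were assumed, the cost would be 0.5–1.3 points of chi-square type I error with an interim on 15 per arm. It would be none if the choosers are blinded, and Fisher's test would stay below 5%. Those figures rest on assumed alpha, response rates, exclusion rates and interim size. The conclusion itself rests on the readable text and on not treating blacked-out text as absent. It would change only if the full text of 9.6 or 9.12 showed that those who settle the Part 2 SAP receive interim results by arm before approving it.

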#### 9.12.1 SUBJECT DISPOSITION

The disposition of all subjects who sign an ICF will be provided. The numbers of subjects screened, enrolled/randomized, completed, and discontinued from the study, as well as the reasons for all discontinuations will be summarized for each part of the study. Disposition and reason for study discontinuation will also be provided as a by-subject listing.

